11.4 STATISTICAL METHODS

Analyses for the primary and secondary efficacy endpoints will be conducted using the mITT population. Analyses for the safety endpoints will be conducted using the safety population. Analyses for the PD endpoints will be conducted using the PD populations. Analyses for the PK endpoints will be conducted using the PK populations. Analyses for the exploratory endpoints will be conducted using the safety population.

In the descriptive analyses, summary statistics for continuous variables will minimally include n, mean, standard deviation (SD), minimum, median, and maximum. For categorical variables, frequencies and percentages will be presented. Graphical displays will be provided as appropriate.

Unless otherwise specified, all baseline values will be defined as the last nonmissing value prior to the first course of alemtuzumab.

11.4.1 Extent of study treatment exposure

Alemtuzumab will be administered by IV infusions in a supervised medical setting at a dose of:

- For patients ≥ 50 kg: 12 mg/day.
- For patients < 50 kg: 0.24 mg/kg/day.

There are two courses. The first treatment course includes 5 consecutive days of infusion, and the second treatment course is administered 12 months after the first treatment course and includes 3 consecutive days of infusion. The numbers and percentages of patients that received each possible level of total dose will be presented in the clinical study report.

11.4.2 Analyses of efficacy endpoints

Analyses for the primary and secondary efficacy endpoints will be conducted using the mITT population.

11.4.2.1 Analysis of primary efficacy endpoint

The number of new or enlarging T2 lesions during continuation of prior DMT (Period 1) and in an equal-length period after the first course of alemtuzumab treatment (Period 2) will be analyzed and compared using a repeated measures negative binomial regression model with GEE. The default log link function will be used to model the expected number of lesions. The robust, sandwich covariance matrix will be constructed assuming an unstructured/exchangeable working correlation matrix.

The primary statistical objective is to test superiority of alemtuzumab versus prior DMT at 5% level of significance. No missing data is expected as the mITT population is restricted to the patients with evaluable data for both Period 1 and Period 2.

11.4.2.2 Analyses of secondary efficacy endpoints

The annualized relapse rate at Year 2 will be estimated using a negative binomial model with robust variance estimation.

The EDSS, descriptive statistics, (eg, percentages of stable/improved/worsened since the end of Period 1) will be calculated.

Descriptive statistics (eg, mean, median, min, max, SD, quartiles) and 95% confidence interval for the means, when appropriate, will be calculated for the change from baseline in cognitive outcomes and QoL measures at each prescheduled, postbaseline assessment visit.

The proportion of patients with new or enlarging T2 lesions during Period 1 and Period 2 will be analyzed and compared using repeated measures logistic regression model with GEE and robust variance estimation. The analyses will be similar to the primary endpoint analyses with the exception of the use of the logit link function and the Bernoulli distribution.

11.4.2.3 Multiplicity considerations

There is no formal hypothesis testing for the secondary efficacy endpoints, therefore the study overall type I error will not need to be adjusted for multiplicity.

11.4.3 Analyses of safety data

11.4.3.1 Adverse events

AE observation period:

- Pretreatment AEs are defined as those AEs that developed or worsened prior to the 1st alemtuzumab dose.
- On treatment AEs are defined as those AEs that developed or worsened after the 1st alemtuzumab dose and until the end of the study (Month 60).
- Posttreatment AEs are defined as those AEs that developed or worsened after the ontreatment period.

On-study period will include pretreatment and ontreatment period. Treatment emergent adverse events (TEAEs) for analysis purpose will include all ontreatment AEs.

The primary analysis of adverse event reporting will be on TEAEs. Pretreatment AEs will be summarized separately.

The incidence of TEAEs (including IARs), AESI, will also be tabulated (frequencies and percentages) by severity, grade/intensity, and relationship to study drug. In tabulating severity of AEs on a per patient basis, the greatest severity will be assigned to a patient when there is more than one occurrence of the same AE with different reported severities. Relationships of the AE to treatment will be categorized as not related, or related. The highest level of association will be reported in patients with differing relationships for the same AE. Actions taken regarding treatment and patient outcome will also be listed.

In addition to IARs analysis above, TEAEs that occurs from start of infusion up to 72 hours postinfusion will be summarized if applicable.

The incidence of AEs leading to study discontinuations will also be summarized by treatment group, with details provided in the listing.

Death: The following deaths summaries will be generated:

- Number (%) of patients who died by study period (TEAE, on-study) and reasons for death summarized on the safety population.
- TEAE leading to death (death as an outcome on the AE e-CRF page as reported by the Investigator) by primary system organ class (SOC), high level group term (HLGT), high level term (HLT) and preferred term (PT) showing number (%) of patients sorted by internationally agreed order of SOC and alphabetic order of HLGT, HLT, and PT.

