
STATISTICAL CONSIDERATIONS
	
Sample size determination:
 
At least 60 patients will be screened in this study to ensure 50 evaluable patients to receive alemtuzumab treatment. This sample size will provide at least 85% power to detect a 50% reduction in the number of new or enlarging T2 lesions during continuation of prior DMT (Period 1) with their number in an equal period after the first course of alemtuzumab (Period 2), assuming 10% dropout and a two-tailed significance level of 0.05. These sample size calculations were simulated using a correlated repeated measures negative binomial regression model with generalized estimating equations (GEE) with robust variance estimation to account for the within-patient correlation in lesion counts between treatment Period 1 (prior DMT) and Period 2 (alemtuzumab).
 
The sample size calculations also assume an overdispersion parameter of 0.7 for both study periods, which is consistent with the variability reported in other paediatric MS studies.
 
Analysis population:
 
Modified ITT (mITT): The primary analysis will be conducted on the population of patients who have received at least 1 dose of alemtuzumab and also have evaluable data for both Period 1 and Period 2.
 
Safety: Safety and tolerability analyses will be conducted on all patients.
 
Primary analysis:
 
The number of new or enlarging T2 lesions during continuation of prior DMT (Period 1) and in an equal length period after the first course of alemtuzumab treatment (Period 2) will be analyzed and compared using a repeated measures negative binomial regression model with GEE.
 
Analysis of secondary endpoints:
 
 Safety and tolerability will be assessed using descriptive statistics and evaluated in comparison to the adult data for the treatment of MS using alemtuzumab. EDSS (descriptive statistics, eg, percentages of stable/improved/worsened since the end of Period 1). The ARR at Year 2 will be estimated using a negative binomial model with robust variance estimation. The change from baseline in cognitive outcomes will be analyzed descriptively.

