	
 • The change from baseline in QoL measures will be analyzed descriptively. • PK serum concentrations and PK parameters will be analyzed descriptively. • PD parameters including lymphocyte subsets will be analyzed descriptively. • Antialemtuzumab antibody results will be analyzed descriptively. • The number and proportion of patients with new or enlarging T2 lesions during Period 1 and Period 2 will be analyzed and compared using a repeated measures logistic regression model. 
Planned Database lock date: A partial database lock will be done after the last patient has completed efficacy assessments including MRI at the end of Period 2. This database lock will allow comparing lesion counts between Period 1 (M-4 to M0) and Period 2 (M4-M8). No formal interim analysis will be performed. The second database lock will be after the last patient has completed the safety monitoring phase (M60).

DURATION OF STUDY PERIOD (per patient)
	
Approximately 5 years 5 months:
 
 • Screening period: maximum 28 days prior to M 4. • Prior DMT phase: approximately 4 months. • Alemtuzumab treatment phase: approximately 2 years. • Safety follow-up period: approximately 3 years.

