Most patients treated with alemtuzumab in controlled clinical trials in MS experienced mild to moderate IARs during or soon after alemtuzumab 12 mg administration. Common IARs include headache, rash, pyrexia, nausea, urticaria, pruritus, insomnia, chills, flushing, fatigue, dyspnea, dysgeusia, chest discomfort, generalized rash, tachycardia, dyspepsia, dizziness, and pain. Serious reactions occurred in 3% of patients including cases of pyrexia, urticaria, atrial fibrillation, nausea, chest discomfort, and hypotension. In addition, anaphylaxis has been reported rarely. Prophylactic use of corticosteroids was useful in alleviating IARs and is part of the recommended prescribing information for alemtuzumab use in MS patients. In addition, modification of the duration of infusion is permitted to help patients tolerate infusions if needed and symptomatic medications such as antihistamines and/or antipyretics were administered often in the studies.

Alemtuzumab treatment increases the risk of autoimmune-mediated conditions. Autoimmune thyroid disorders occurred in 36 % of patients in clinical trials in MS through 4 years following first exposure. Observed autoimmune thyroid disorders included hyperthyroidism and hypothyroidism, which occurred at similar rates. Serious thyroid related events occurred in <1% patients. No consistent pattern was observed with regards to time of onset after treatment initiation, although the highest incidence of thyroid adverse events (AEs) was observed in Year 3 after the first treatment course. Therefore, as part of the risk minimization strategy for autoimmune disorders, thyroid function tests must be obtained prior to the initiation of alemtuzumab treatment and every 3 months thereafter until 48 months following the last infusion. This will allow the timely detection and treatment of thyroid disorders for patients treated with alemtuzumab.

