6 STUDY DESIGN

6.1 DESCRIPTION OF THE STUDY

This is an open-label, rater-blinded, single-arm, before and after switch study of efficacy, safety and tolerability of alemtuzumab in paediatric patients from 10 to <18 years of age with RRMS with disease activity on prior DMT.

The study will consist of:

- **Screening period** (0-28 days prior to M-4) - Patients and parents will receive information on the study and on alemtuzumab. Inclusion/exclusion criteria will be reviewed. After informed consent signature, screening assessments for eligibility will be performed. Screening assessments may require more than one visit within the screening period which may last a maximum of 28 days.
- **Prior DMT phase (approximately 4 months): M-4 to M0**
 - **Eligibility confirmation visit:** At the end of the screening period (at M-4) patients/parents will come to the site to confirm patient is eligible for the study. Investigator will check that all assessment allow patient inclusion. During this visit patients will be reminded to continue their prior DMT (limited to interferon or GA only).
 - **From M-4 visit to D-14 to D-7:** Phone calls (approximately every month) will be done, to remind patients to continue on their DMT and check patient status.
 - **Day -14 to D-7 visit:** Investigator will confirm patient is eligible for alemtuzumab administration and will tell the patient to discontinue current DMT 7 days prior to administration of first dose of alemtuzumab at Month 0.
- **Alemtuzumab treatment phase** (approximately 2 years) – This phase starts with administration of first dose of alemtuzumab at M0, after discontinuation of current DMT, and ends at M24. The second dose of alemtuzumab will be administered at M12. The MRI based primary efficacy endpoint will be assessed over a 4 month period during this phase compared to an equal period during the prior DMT phase.

Note: end of treatment phase (EOTP) refers to the end of the alemtuzumab treatment phase (see graphic study design [[Section 1.1](#)]).
- **Safety monitoring phase** (approximately 3 years) – Additional safety follow-up and monitoring for all patients treated with alemtuzumab will be conducted during this phase to yield a total of 5 years of follow-up since first alemtuzumab treatment, including 4 years post last treatment with alemtuzumab.

Note: end of study (EOS) refers to the end of the safety monitoring phase (see graphic study design [[Section 1.1](#)]).

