Concomitant use of systemic corticosteroids for the treatment of MS relapse is allowed during this period.

Safety monitoring phase

The safety of MS disease-modifying drugs in patients who receive alemtuzumab has not been established. Alemtuzumab treatment may have long-lasting, unknown effects on a patient's immune system. Concomitant therapy with any disease-modifying MS treatments following treatment with alemtuzumab has not been studied in a controlled study conducted by Sanofi Genzyme. Investigators should consider the potential for adverse effects associated with subsequent or concomitant treatment with cytotoxic or immunosuppressant drugs in patients who have received alemtuzumab.

Participating patients are prohibited from use of any investigational MS therapy.

It is investigator criteria to determine if the patient needs to be treated with another DMT, and in which case the patient will be discontinued from the study.

Concomitant use of systemic corticosteroids for the treatment of MS relapse is allowed during the course of the Study. Relapses may be treated with systemic corticosteroids if clinically necessary and as per Investigator judgment in doses appropriate for paediatric population.

The use of systemic corticosteroids or adrenocorticotrophic hormone within 2 weeks prior to MRI assessment is not permitted due to potential interference with MRI assessment.

It is recommended that patients complete local immunization requirements at least 6 weeks prior to treatment with alemtuzumab. The ability to generate an immune response to any vaccine following alemtuzumab treatment has not been studied.

The safety of immunization with live viral vaccines following a course of alemtuzumab treatment has not been formally studied in controlled clinical trials in MS. Live vaccines must not be administered to MS patients who have recently received a course of alemtuzumab. Also, some experts urge caution in using live pathogen vaccinations in people with MS (National MS Society web site).

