11.3 ANALYSIS POPULATIONS

11.3.1 Modified Intent-to-treat population

Modified Intent-to-treat (mITT): The primary analysis will be conducted on the population of patients who have received at least 1 dose of alemtuzumab and also have evaluable data for both Period 1 and Period 2. The mITT population will be used for the analyses of the primary and secondary efficacy endpoints.

11.3.2 Safety population:

The safety population consists of patients who have received at least 1 dose of alemtuzumab. Safety and tolerability analyses will be conducted on all patients in the safety population. At the first database lock after the last patient has completed efficacy assessments including MRI at end of Period 2, some patients will have follow-up beyond the end of Period 2, all available information will be used for safety and tolerability analyses.

PK: the PK population consists of patients who have received at least 1 dose of alemtuzumab and also have evaluable PK data.

PD: the PD population consists of patients who have received at least 1 dose of alemtuzumab and also have evaluable PD data.

For patient study status, the total number of patients in each of the following categories will be presented in the clinical study report using a flowchart diagram or summary table:

- Screened patients.
- Screened failure patients and reasons for screen failure (if data is available).
- Number and percentage of patients who did not complete prior DMT phase, with corresponding reasons.
- Number and percentage of patients who did not complete Period 2 with alemtuzumab, with corresponding reasons.
- Number and percentage of patients who did not complete safety monitoring phase (will be included in final study report only), with corresponding reasons.

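### Adverse events are summarised as crude percentages over unequal follow-up at the first lock; set beside a cumulative adult figure without time matching, they would understate paediatric risk

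*Protocol*

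**What the plan says.** Protocol section 11.4.3.1 states that the incidence of treatment-emergent adverse events (TEAEs) and adverse events of special interest (AESIs) "will also be tabulated (frequencies and percentages) by severity", and by relationship to study drug. The TEAE window runs from the first alemtuzumab dose to Month 60, with no cut at a common follow-up time.

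On the first database lock, section 11.3.2 says that "some patients will have follow-up beyond the end of Period 2, all available information will be used for safety and tolerability analyses". That lock falls when the last patient finishes Period 2, at M8. The final lock comes after the last patient completes M60, and section 6.1 plans follow-up "to yield a total of 5 years of follow-up since first alemtuzumab treatment, including 4 years post last treatment with alemtuzumab".

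The clinical trial summary says that safety will be "evaluated in comparison to the adult data for the treatment of MS using alemtuzumab", and section 9.6 repeats this. Neither place gives a method, a time point or an adult data cut. The only late autoimmune figure in the protocol with a time attached is in section 4: "Autoimmune thyroid disorders occurred in 36 % of patients in clinical trials in MS through 4 years following first exposure". The same paragraph puts the highest thyroid incidence in Year 3.

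Section 11.4.3.2 does use a Kaplan-Meier estimate for one safety outcome, time to first ALT elevation above 3 times the upper limit of normal.

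**The concern.** A crude percentage depends on how long patients were observed as well as on their risk. At the first lock the denominator mixes patients seen for about 8 months with patients seen for much longer. A cumulative adult figure through 4 years has a different time base, so the two cannot be read against each other.

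This matters because section 5.1 places safety and tolerability in the primary objective alongside efficacy, and the first lock is where the primary endpoint is analysed. The first safety summary will therefore accompany the main efficacy result. A reader who sees a thyroid percentage well below the adult 36% could conclude that children are at lower risk, when the gap may come only from shorter observation.

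**Working it through.** **Inputs from the protocol.** Adult thyroid disorders: 36% through 4 years, highest incidence in Year 3 (section 4). Follow-up of the last patient at the first lock: 8 months from first dose (sections 6.1 and 6.3). Planned follow-up at the final lock: 60 months. About 50 patients.

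**Assumptions, not in the protocol.** Children have exactly the adult risk. The 36% is read as a true cumulative risk. Accrual is uniform over 1 to 4 years. The hazard is either constant or peaks in Year 3 with yearly weights 1:2:3:2:1. Dropout is exponential, with 0 to 50% gone by M60.

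**Step 1: hazard.** The 36% is an observed result with no inputs to rebuild it, so it is taken as given. Cumulative hazard to 4 years = −ln(1 − 0.36) = 0.446. Spread evenly, λ = 0.446/4 = 0.1116 per year.

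**Step 2: first lock.** Follow-up t is uniform from 8 months (0.667 years) to 0.667 + A years, where A is the accrual length. Under a constant hazard:

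expected crude proportion = 1 − [exp(−0.667λ) − exp(−(0.667 + A)λ)] / (λA)

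For A = 2: 1 − (0.9283 − 0.7427)/0.2231 = 0.168.

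| Accrual (years) | Mean follow-up (years) | Constant hazard | Year 3 peak |
|---|---|---|---|
| 1 | 1.17 | 12.2% | 7.4% |
| 2 | 1.67 | 16.8% | 12.7% |
| 3 | 2.17 | 21.1% | 18.3% |
| 4 | 2.67 | 25.1% | 22.8% |

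Every entry lies below 36%, by 11 to 29 percentage points. In 50 patients, 16.8% is about 8 cases and 36% is 18.

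**Step 3: final lock.** The crude proportion to M60 is the integral of the hazard times the probability of still being event-free and in the study. With no dropout and a constant hazard it is 1 − exp(−5 × 0.1116) = 42.8%.

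| Dropout by M60 | Constant hazard | Year 3 peak |
|---|---|---|
| 0% | 42.8% | 39.5% |
| 20% | 38.7% | 35.6% |
| 40% | 34.3% | 31.3% |
| 50% | 31.8% | 29.0% |

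Against the 4-year 36% the crude figure runs from about 7 points above to 7 points below.

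**Step 4: what a matched estimate would show.** With non-informative censoring, a Kaplan-Meier estimate at any time the data reach recovers the cumulative risk at that time. Under a constant hazard that is 10.6% at 1 year, 20.0% at 2 years and 36% at 4 years, whatever the accrual. A 48-month estimate is reachable at the first lock only if accrual exceeds 48 − 8 = 40 months. Before that, the comparison must use an earlier time for both populations.

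**The case against.** The strongest reply is that the protocol never says a first-lock percentage will be placed beside the 36%. It promises an adult comparison without a method. Section 9.6 links that comparison to safety for up to 4 years after the last dose, which points to complete follow-up, and the stated purpose of the first lock is the lesion comparison. The 36% is background in the introduction and is not named as a benchmark. This stands, so the point is conditional. It keeps its force because percentages are the only incidence summary stated for adverse events in general, and section 11.3.2 expressly uses the first lock for safety.

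A second reply is that person-time rates or Kaplan-Meier estimates may be in the statistical analysis plan, which is not shown. Their absence from the protocol alone would be no finding. The point rests instead on what the protocol does fix: percentages, pooled unequal follow-up and an adult comparison with no common time.

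Two stronger readings are tempting and are not supported:

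- **That crude percentages understate risk throughout the trial.** At the final lock all patients are planned to reach M60, and section 10.3.4 keeps those who stop treatment under follow-up. Follow-up is cut short only by withdrawal or by a need for another disease modifying therapy, "in which case the patient will be discontinued from the study" (section 8.8). The rate is not given. Five years set against a 4-year adult figure can err upward, as it can against adult figures from trials of up to 2 years, such as the 71% for infections in section 4.
- **That immune thrombocytopenia and nephropathy are affected in the same way because they also occur late.** The protocol gives onset timing for thyroid disorders only, and even there it reports no consistent pattern beyond the Year 3 peak.

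It is also fair that the safety analysis is descriptive and small. With serious immune thrombocytopenia at about 1% in adults, half an event is expected in 50 patients, and the choice of estimator hardly matters there.

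**Conclusion.** The point holds in a limited form. At the first lock, the stated summary cannot be read against a cumulative adult figure. For thyroid disorders it would give about 17%, 21% or 25% against 36% with no difference in risk, under a constant hazard and assumed uniform accrual of 2, 3 or 4 years. Across all the scenarios tested the range is 7% to 25%. The size depends on accrual length and hazard shape, which the protocol does not give. The direction was the same in every scenario.

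At the final lock the direction is open and depends on an unstated discontinuation rate. No timing claim is made for immune thrombocytopenia or nephropathy. A reader might infer that the sponsor plans to contrast first-lock percentages with the 36%; the protocol does not say so, and the finding is that nothing in it prevents such a contrast. This is a cheap improvement to the safety analysis.

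**What to change.** Keep counts and percentages as description. Add to section 11.4.3.1 that, at both locks, AESIs and any TEAE compared with adult data will also be reported as rates per 100 patient-years and as Kaplan-Meier or cumulative incidence estimates, by year since first dose. The rates should be split by year because a single overall rate would still mix early and late risk if the hazard peaks in Year 3. State that comparisons with adults will be made only at matched follow-up time, and name the adult data source and time points. Patients who leave the study to start another therapy should be counted and shown, since their censoring may be informative.

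The cost is a few sentences and a few tables. Section 10.4.3 already requires the onset date of each event, so no new data are needed and no clinical procedure changes. The downside is imprecision: at 50 patients and 36%, the 95% half-width is 1.96 × √(0.36 × 0.64/50) = 13 percentage points even with complete follow-up, and intervals at late times will be wider at the first lock.
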